FluSAFE: Flu SMS Alerts to Freeze Exposure

ClinicalTrials.gov ID: **NCT03274310**

Document date: May 4, 2020

SPECIFIC AIMS

We propose to conduct a randomized controlled trial assess whether a scalable, text message-based educational intervention triggered by text message-based surveillance for influenza-like illness (ILI) in households with one or more children can decrease laboratory-confirmed influenza transmission.

Influenza infection results in an estimated 31 million outpatient visits, 55,000 to 974,200 hospitalizations (2014-15 estimate: 974,206), and 3000 to 49,000 deaths (2014-15 estimate: 49,006) annually.¹⁻³ Membership in a household in which someone else has influenza is the major risk factor for contracting influenza.⁴⁻⁷ The household secondary attack rate (SAR) is as high as 19% based on laboratory-confirmed influenza and 30% based on symptoms.⁶⁻¹⁴ Non-pharmaceutical preventive measures including education have been found to decrease influenza transmission.¹⁵ For example, in one study during the 2009 influenza A H1N1 pandemic, having had a household discussion about preventing transmission was significantly associated with decreased SAR.⁷ Most transmission occurs early in an illness,^{7,10,13} and it has been demonstrated that non-pharmaceutical interventions are effective only if started within 36 hours of index case symptom onset.^{16,17} Yet, most interventions are delayed because they are not initiated until care is sought.^{16,17} In one study, less than 30% of households were identified within 36 hours when an index case was diagnosed at a medical visit.¹⁶ We reasoned that use of home surveillance with text-message symptom reporting to trigger an educational intervention has the potential to overcome delays in implementing preventative behaviors.

In previous work, we demonstrated in one primarily Latino, urban sample, that text messaging by family members can be used to rapidly identify members with ILI/acute respiratory infections (ARI) early in an illness.¹⁸ This approach to early identification would enable implementation of an educational intervention targeted to the 36-hour timeframe. Providing education within a text message is a proven successful strategy to influence behavior.¹⁹⁻²² Using text message surveillance to trigger a novel educational intervention also allows inclusion of both medically and non-medically attended index cases, a key element in reducing influenza SAR since less than one-third of persons with laboratory-confirmed influenza seek medical care.¹⁸ Text messaging itself is scalable, low-cost, and can be used in low literacy populations.²³ However, using text-message based surveillance to trigger a real-time text-message behavioral educational intervention to decrease household influenza transmission has not been assessed. In evaluating the impact of this intervention strategy, the primary outcome will be laboratory-confirmed influenza. The primary outcome will be determined using self-swabs among household members to detect SAR, including asymptomatic infection and medically- and non-medically attended illness. We have successfully piloted self-swab collection.

Aim: To assess the impact of an educational intervention delivered by text messaging on transmission of influenza within households

Primary Outcome Hypothesis: Educational text-messages will reduce laboratory-confirmed influenza household transmission from 12% to 5%

Secondary Outcome Hypothesis: Educational text-messages will reduce ILI transmission from 23% to 11%

Exploratory Aim: To compare the yield of text message ILI/ARI surveillance among subgroups in a diverse, community sample

Hypothesis: Response rates to text messages will be similar among different sociodemographic groups.

We will enroll and randomize 400 households (n=~1500 individuals) with ≥ 1 child recruited from four contiguous communities in New York City 1:1, stratified by community, to receive surveillance-only vs. surveillance plus text message educational intervention. We will have 88% power to detect a decrease in influenza SAR from 12% to 5%. These percentages are derived from the paper by Cowling *et al.*, reporting a reduction from 12% to 5% between hand hygiene and usual care arms in SAR for influenza when a non-text message-based behavioral intervention was started ≤ 36 hours of index illness onset.¹⁶ For surveillance, households in both arms will receive text messages 3x/week during each influenza season (Nov-Mar) and report household members with ILI/ARI symptoms. For those in the educational intervention arm, when an ILI/ARI is reported, educational text messages will be sent targeted to decrease household transmission.

Both arms will obtain one self-swab of the index case, and self-swabs of all other household members on days 3 and 5 from index onset.^{7,10,13,24} Swabs will be returned via postage-paid envelope and analyzed using an FDA-approved reverse-transcriptase multiplex PCR assay to identify influenza, including sub-types, as well as other viral respiratory pathogens, e.g., parainfluenza etc. We will also collect symptom reports from all household members. The primary outcome will be SAR of laboratory-confirmed influenza. Secondarily, we will assess SAR based on ILI/ARI symptoms, and of non-influenza viruses. Response rates will be compared between arms and by demographic factors (age, education, race/ethnicity). Trial results could provide support for text-based strategies to reduce influenza transmission.

B. RESEARCH STRATEGY

SIGNIFICANCE

Impact of Influenza: Influenza infection results in an estimated 31 million outpatient visits, 55,000 to 974,200 hospitalizations (2014-15 estimate: 974,206), and 3000 to 49,000 deaths (2014-15 estimate: 49,006) annually.¹⁻³ The burden of influenza also includes high cost from direct medical expenses, days lost from work or school,²⁵ and inappropriate use of antibiotics.²⁶ Children and adolescents 6 months-18 years old are at increased risk of influenza morbidity and mortality, and influenza is one of the most common causes of hospitalization for the pediatric population.¹ School-aged children and adolescents also serve as an important reservoir, transmitting influenza to household members.^{1,27}

Household Transmission of Influenza. Membership in a household in which someone else has influenza is the major risk factor for contracting influenza.⁴⁻⁷ The secondary attack rate of influenza in a household is as high as 19% based on laboratory-confirmed seasonal and pandemic influenza, and as high as 30% based on symptoms for ILI/ARI.⁶⁻¹⁴ Non-pharmaceutical preventive measures including education have been found to reduce household transmission.¹⁵ One study conducted during the 2009 H1N1 pandemic found that having had a household discussion about how to prevent transmission was the only household-level factor significantly associated with decreased secondary attack rates.⁷ However, since most transmission occurs in the first few days of illness,^{7,10,13} it is important that the intervention occur as soon as possible after onset of symptoms in the index case. Cowling *et al.* demonstrated an effect of non-pharmaceutical intervention (hand hygiene alone and hand hygiene plus face mask) only when initiated within 36 hours of symptom onset in the index case.¹⁶ Seuss *et al.* also found an impact of mask or mask plus hand hygiene only in households for which the intervention was also started within 36 hours.¹⁷ Interventions will be delayed when they depend on the index case seeking care.^{16,17} In Cowling's study, less than 30% of households were identified within 36 hours of onset based on identifying index cases at a medical visit. During the 2009 H1N1 influenza A pandemic, surveillance based on medical visits for ILI was not completely useful for detecting or monitoring the outbreak due in part to the lack of timeliness of visits.²⁸ These failures to capture cases within 36 hours arise from two factors: time between onset of ILI and seeing a medical provider, and cases that are not medically attended at all. We reported that less than one-third of persons with laboratory-confirmed influenza in a community surveillance study sought medical care.¹⁸ Influenza cases have the potential to transmit infection to household members during the first 36 hours of symptoms; the earlier in this period and the higher the proportion with ILI who receive an educational intervention, the greater the potential to reduce transmission.

Text Messaging and Community-based ILI/ARI Surveillance. To address the limitations of rapid identification of cases based on medical attendance, several studies have had people report via an automated telephone system,²⁹ but this strategy depends on participants actively remembering to initiate the report. Others have used email, but use may differ by demographics and may not be feasible in diverse populations.³⁰ While others have used Internet surveillance,³¹ or other sources like Google Flu Trends, Twitter³²⁻³⁴ or crowdsourcing,³⁵ these data are only available in aggregate. Furthermore, they cannot be verified, be used to measure transmission, nor determine an infectious etiology since respiratory samples are not taken. In addition, internet-based communications may have HIPAA limitations.³⁶

Text messaging, however, could facilitate rapid surveillance and data collection from large numbers of participants from diverse populations by using a personalized, patient-centered approach. Text-messaging is not internet-based and does not have internet-related HIPAA limitations. Currently, 90% of adults in the U.S. own a cell phone, with high rates in both minority and non-minority populations (90% White, 90% Black, 92% Latino).²³ Smart phone use, although increasing, is lower (64%).²³ Text messaging can also accommodate different languages, and messages can be tailored to each participant by using response algorithms. Text-messaging can be used effectively in low-literacy populations.¹⁸⁻²² Another advantage of text messaging is its scalability. After the initial investment to develop the platform, the cost of each additional message is negligible, allowing large numbers of participants to be monitored simultaneously and serially over time. Text messaging can also be centralized and standardized across large geographic areas, allowing surveillance and assessment of distinct demographic subgroups or geographic areas while still maintaining the economy of centralized data collection, management, and analysis. Finally, it allows capture of both medically-attended and non-medically attended disease.

[figure not shown]
As part of an ongoing community-based study funded by CDC, we have demonstrated the feasibility of using text messaging to conduct ILI/ARI surveillance in one primarily Latino, urban neighborhood community.¹⁸ During the first three years of the study, 62,650 text messages were sent to households and responses were received for 48,308 (77.1%). The response rate did not decrease over time. The majority (88.9%) of responses

were received within 4 hours of messages being sent and 96.2% responses were received within 12 hours (section- preliminary studies). Based on our community study, the CDC has now included the use of text message surveillance as part of their pandemic influenza research plans.³⁷

Text Message Reporting and Real-time Behavioral Intervention to Reduce Transmission. While text messaging surveillance can rapidly assess if someone in a household is ill, one potential benefit of this type of surveillance that has not yet been studied is the ability to trigger a real-time educational intervention to decrease transmission by exploiting this rapid identification in order to decrease transmission from both medically-attended and non-attended index cases. Providing education within a text message is a proven successful strategy to influence behavior. We have demonstrated the impact of text message educational reminders to improve influenza vaccination as well as other vaccinations.¹⁹⁻²² Text messaging has also been used for other behavioral interventions such as smoking cessation.³⁸

The **Health Belief Model** provides a conceptual basis for the intervention we are proposing to test.^{39,40} According to this model, four main factors affect health-related behaviors: perceived susceptibility of

Figure 1: Health Belief Model and Behavioral Intervention to Decrease Respiratory Virus Transmission (modified from Rosenstock et al)

contracting the disease; perceived severity of the disease; perceived barriers to adoption of a behavior to avoid the disease; and the perceived effectiveness of the behavior. While the model is usually focused on an individual's behavior to protect him/herself from developing a disease, for infection transmission, the model can also include behaviors to protect oneself and other household members. Lastly, a cue to action must be present to trigger the behavior.

This conceptual framework will be used to design educational information to be sent within text messages (cue to action) (Figure 1). First, messages will include information explaining that an ill individual can transmit the viral respiratory illness

to their household members, and that transmission could be harmful to their household members. Next, messages will include easy to implement behavioral suggestions, and finally will include information regarding the effectiveness of these behaviors. We will also include an interactive component, thereby allowing users to gain further information and enhance engagement.^{20,41} Consistent with **health communication theory**, these messages will come from a credible source (e.g. the family's health care provider), be in easily understood language, and will recommend behaviors that can be immediately and easily implemented.^{42,43}

Disadvantaged Populations and Households with Children are at Higher Risk for Influenza. The study population will include disadvantaged and other high-risk populations. Understanding the impact of an intervention to decrease influenza household transmission in a low-income, urban population may be particularly important as they may be at higher risk for infection and transmission due to overcrowding.^{44,45} In addition, they are at greater risk of having non-medically attended disease as being low-income, Latino, publicly insured, foreign born and having a lower education level are factors associated with lower likelihood of having a primary health care provider and seeking care for illness.^{18,46} Also, each household will have at least one child which potentially can lead to higher infection risk.²⁷ Thus, the risk and impact may be greater, and strategies that work in such populations – such as text messaging – need to be tested.

Thus, the significance of our proposed trial arises from the high secondary attack rate of influenza in households with children, the high morbidity and cost of influenza, and the use of new HIPAA-compliant communications technology, specifically text messaging, that is low cost, scalable, and usable in high-risk populations, to implement home surveillance-linked text-message based educational and behavioral intervention. No trials of this approach have been reported or are being conducted to our knowledge.

INNOVATION

This study is innovative in four ways. (1) It will assess the effectiveness of delivering a real-time text-message-based behavioral intervention to decrease influenza transmission within households. (2) It will also determine if the intervention decreases transmission of other respiratory viruses. (3) It will use text messaging for large-scale ILI/ARI surveillance among varied sociodemographic groups and assess group-specific response rates. (4) It will obtain self-swabs from participants with ILI/ARI to detect respiratory pathogens.

First, while we have previously demonstrated the effective use of text messaging surveillance for ILI, we have not assessed coupling an educational intervention targeted at decreasing influenza transmission to this approach to surveillance. We are not aware of any trials of this strategy for reducing influenza SAR.

Second, while the primary target for most surveillance efforts is influenza, because of the affordability and availability of commercially available multiplex PCR kits, we will be able to assess the impact of the intervention on other non-influenza respiratory pathogens, which are more common than influenza.¹⁸ Thus, the use of text messaging to provide a real-time health behavioral intervention during respiratory illness could provide new insights into prevention strategies for non-influenza viral pathogens. This is also novel.

Third, while we are successfully using text messaging for ILI/ARI surveillance in a predominately Latino community, it is not known if it will be as effective in other populations included in this study-- African-Americans and White, non-Latinos of varying sociodemographic status. In addition, in our ongoing MoSAIC study, families are very closely followed, which may decrease the generalizability of their text response rates. In this proposed study, we will also assess the feasibility of using text messaging in a more diverse and geographically widespread population with less frequent contact with research staff to demonstrate its feasibility, effectiveness, and potential scalability.

Finally, the feasibility of collecting respiratory tract specimens is limited by the time and effort required for an ill individual to come to a central site to have a sample taken, as done in some studies,¹⁰ or the time and expense required for staff to go to an ill person's home to obtain a sample as done in our ongoing study. We and others have shown that self-swabs can be used to identify respiratory pathogens during acute illness, (section preliminary studies).⁴⁷⁻⁵⁰ However, a study coupling text message ILI/ARI surveillance with self-swabs as the mode of data collection has not, to our knowledge, been conducted among participants from varied socio-demographic populations.

APPROACH

PROJECT TEAM: This interdisciplinary research team has expertise and experience in all key study aspects including community-based sample recruitment and retention, community ILI/ARI surveillance, text message surveillance, using multiplex reverse-transcriptase polymerase chain reaction (RT-PCR), and text messaging-based behavioral interventions. The investigators also have a long history of collaborative work.

[name], the contact PI, has expertise in monitoring ILI/ARI in a community household sample. She is PI of a CDC funded grant, the MoSAIC study (U01P000618), which includes community-based surveillance for ARI/ILI using text messages.^{18,47,51} Additionally, she has provided expertise to the CDC on pandemic influenza planning including community surveillance and conducted two studies of the 2009 influenza A H1N1 pandemic.^{52,53} She was PI on an NIH funded grant, the ACURI study (RC1 MD004109), an educational intervention to improve care for ARI,⁵⁴ and is experienced with the use of text messages for vaccine adverse event surveillance, and for other behavioral interventions including promoting vaccination,¹⁸⁻²² including serving as PI on four grants (R01HS022677, R40MC17169, U01IP000313, U01IP000618).

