approached to participate) in our previous studies.^{18,29,54} The project coordinator will assess the first eligibility criteria (number of household members, child <18 years-old in household and Spanish/English-speaking). If the household is eligible, the coordinator will ask who is the primary caregiver of the children in the household and then ask if that person has a cellphone with text messaging and if they are willing to be the household reporter, as well as confirm that they and the household are not planning on moving in the next year. If these criteria are met, a home visit for enrollment will be scheduled. The household reporter will provide written consent, which will include being the household reporter and sending and receiving text messages. Other household members will be provided with an information sheet in English or Spanish explaining the study and the request for self-swabs from both ill participants and asymptomatic participants. In our text message surveillance study, these procedures were approved by the Columbia University Medical Center Institutional Review Board. Each study participant will be given a unique study ID coded to their household. Multiple other sources of contact information, if available, will be collected for the household reporter including landline and email address.

Randomization Procedures. On study enrollment, we will randomize 400 households (100 from each community) 1:1 to surveillance + education vs. surveillance-only arm, stratified by community and sampling site. Randomization will be conducted by the programmer under the supervision of the study statistician using permuted blocks ensuring balance between the arms. The programmer will enter the study arm the household is randomized to into the text messaging platform database, but arm assignments will not be visible to other research staff. Thus, the statistician and research staff will be blinded to arm.

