Annual home visits will be made to all enrolled households wanting to continue the next respiratory season to facilitate retention and participation, answer questions, ensure contact information remains correct, update household composition changes, and provide swab kits. Households that continue to meet eligibility criteria (Table 2) may continue into the next respiratory season. Households will receive \$50 on enrollment and \$25 at this re-enrollment visit; this will aid with enrollment and retention. Participants will also receive compensation for reporting and returning self-swabs as outlined below. If a household no longer meets eligibility criteria during a season or if are lost to follow-up, we will replace households in the same season if there are ≥2 months left in the influenza season or the next year if there are <2months left. Households that leave the study will be replaced using the same procedures as for the baseline sample using 1:1 randomization. Based on previous studies, we expect 10-20% of households to be replaced yearly.^{18,29,67}

TEXT MESSAGE SURVEILLANCE FOR ILI/ARI

Both arms (surveillance + education vs. surveillance-only) will receive text messages to perform surveillance of household members for ILI/ARI. The surveillance period will run November through March each year. We have chosen that period since for the past 9 years (with the exception of the 2009 influenza A H1N1 pandemic) the earliest onset of influenza in these communities has been in November and we have seen the vast majority of influenza cases by March.^{18,68} If there are unusual influenza patterns, we will be able to start sample collection earlier or end it later. During the surveillance period, each household reporter in all households will automatically receive text messages three-times a week from the text messaging system (a.k.a. *research staff-generated messages*) asking if any household member has symptoms included in the study case definitions for ILI/ARI and asked to respond whether or not anyone is ill (Figure 3). Households will be texted on a Monday, Wednesday and Friday schedule to optimize days between reporting. We have chosen this schedule so that intervention can start within 36 hours of onset. Messages will be sent in English or Spanish based on the

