We will use Pearson chi square to assess relationship between text message response rates and community, reporter's race/ethnicity, insurance and education. This will be defined as number of responses received per message sent. If more than one variable is significantly related to reporting rates ($p<0.1$), we will develop multivariable logistic models to assess this relationship. We will also assess response rates by arm.

SAMPLE SIZE AND POWER

We have based our sample size on the primary outcome. With 200 households per arm and an average of 3.8 persons/household, we will have 88% power to detect a decrease in secondary attack rates of laboratory-confirmed influenza from 12% (surveillance-only) to 5% (surveillance + education), based on type I error of 5% and an intracluster correlation coefficient of 0.29. The intracluster correlation, expected transmission rates for the surveillance-only arm, and effect size are derived from the paper by Cowling *et al.*, reporting a reduction from 12% to 5% between the hand hygiene and usual care arms in SAR when a non-text message based behavioral intervention was started at ≤ 36 hours of illness onset in the index case using laboratory-confirmed influenza as an outcome.¹⁶ In the MoSAIC study, secondary attack rates for laboratory-confirmed influenza have been 16.6% therefore an expected rate of 12% in the surveillance-only arm is conservative. We will also be powered for our secondary outcome; we will have 91% power to detect a decrease in symptomatic ILI/ARI from 23% to 11%.¹⁶ If we lose 80 households (20%) per season, we will still have at least 80% power to detect the decreases in both the primary and secondary outcome as above, even without household replacement.

POTENTIAL CHALLENGES AND SOLUTIONS Table 3

Challenge	Solution
1. Recruitment and retention	In our previous community studies retention was excellent. In our MoSAIC study, 75.9% of households recruited in year 1 were still in the study in year 3.
2. Non-representative sample	Since eligibility criteria include ≥ 3 members and ≥ 1 child, the sample will not be fully representative of the communities. However, the benefits of these inclusion criteria include higher likelihood of infection and transmission.
3. Reporting bias	3x/a week texting will decrease recall bias. We have shown under- and over-reporting to be low and confirmed the validity of household symptom self-reports.

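### The exploratory hypothesis of similar text response rates is assessed with a message-level chi-square test, which cannot show similarity and ignores clustering of messages within households

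*Combined protocol and SAP*

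**What the plan says.** The exploratory aim in the Specific Aims is to compare the yield of text surveillance across subgroups. Its hypothesis is that "Response rates to text messages will be similar among different sociodemographic groups".

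The Statistical Plan, under Exploratory Aim, gives the analysis: "We will use Pearson chi square to assess relationship between text message response rates and community, reporter's race/ethnicity, insurance and education". The rate is then specified: "This will be defined as number of responses received per message sent". A p<0.1 screen follows. "If more than one variable is significantly related to reporting rates" at that level, multivariable logistic models are to be built. Response rates by arm are also to be assessed.

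For this aim the plan states no margin for similarity, no confidence-interval criterion and no term for household. By contrast, the primary analysis in the same Statistical Plan names a mixed model for clustering within a household. The Sample Size and Power section covers only the transmission outcomes.

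**The concern.** There are two separate problems.

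1. **The test does not match the hypothesis.** The claim is one of similarity, but the null hypothesis of a chi-square test is no difference. Failing to reject may only mean that the data are imprecise. Rejecting may reflect a gap too small to matter. Without a margin, neither result settles whether rates are similar.
2. **The unit of analysis is the message.** One reporter answers about 65 surveillance texts a season, and some reporters are habitually more responsive than others. A chi-square on message counts ignores this, so its standard errors are too small and its p-values too low.

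The Innovation section lists group-specific response rates among the trial's four novel features. The risk is that the trial reports group differences that are only household-to-household variation, or reports similarity on the strength of a non-significant p-value.

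**Working it through.** **Inputs from the documents**
- Households: "we will randomize 400 households (100 from each community) 1:1" (Randomization Procedures).
- Frequency: "Households will be texted on a Monday, Wednesday and Friday schedule", from November through March (Text Message Surveillance). That is 151 days, so 151/7 × 3 = 64.7 texts per household per season.
- Response rate: the team's earlier text-surveillance study reports 77.1%. Check: 48,308/62,650 = 77.1%.

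**Assumptions**
- Three seasons. Table 4 places surveillance in months 13 to 41. If month 13 is a November, month 41 is a March and exactly three seasons fit, but the calendar start is not given. One season is shown as the other end of the range.
- Intracluster correlation (ICC) of message response: 0.05 to 0.30. The documents give none. The only ICC stated ("based on type I error of 5% and an intracluster correlation coefficient of 0.29") concerns infection among household members and is not borrowed here.
- Equal message counts per household.

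**Step 1. Messages.** Per household: 64.7 × 3 = 194. In total: 194.1 × 400 ≈ 77,700. Per community: about 19,400 (6,470 in one season).

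**Step 2. Smallest gap between two communities that a message-level test calls significant at 0.05.** Threshold = 1.96 × √(2 × 0.771 × 0.229 / n).
- Three seasons: 1.96 × √(0.3531/19,414) = 1.96 × 0.00426 = 0.84 points. A gap of 0.80 points falls just short (p = 0.06).
- One season: 1.96 × √(0.3531/6,471) = 1.96 × 0.00739 = 1.45 points.

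**Step 3. False rejection when true rates are equal.** Design effect D = 1 + (m − 1) × ICC, where m is messages per household. For two groups, the rejection rate at nominal 0.05 is 2 × [1 − Φ(1.96/√D)]. For the four-community test, the 3-df critical value 7.815 is divided by D.

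| Seasons | ICC | D | Two groups | Four communities |
|---|---|---|---|---|
| 3 | 0.05 | 1 + 193.1 × 0.05 = 10.7 | 55% | 87% |
| 3 | 0.10 | 20.3 | 66% | 94% |
| 3 | 0.30 | 58.9 | 80% | 99% |
| 1 | 0.05 | 4.2 | 34% | 60% |
| 1 | 0.30 | 20.1 | 66% | 94% |

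Even at an ICC of 0.01 over three seasons (D = 2.9), the two-group rate is 25%.

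**Step 4. Precision once households are the unit.** For two communities of 100 households, the 95% half-width is 1.96 × SD × √(2/100), where SD is the between-household standard deviation of response rate (assumed 15 to 30 points).
- SD 15: 4.2 points.
- SD 30: 8.3 points.

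The standard error of a difference between communities is then 2.1 to 4.2 points, so an observed gap of 0.84 points lies well within chance variation.

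The two assumed ranges differ. By ICC = SD²/(0.771 × 0.229), an SD of 15 to 30 points corresponds to an ICC of about 0.13 to 0.51. An ICC of 0.05 to 0.30 over three seasons gives half-widths of 2.7 to 6.4 points.

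**Step 5. What a margin could deliver.** Take ±10 points purely as an illustration, with equal true rates and the whole 95% interval required to lie inside. For one pair of communities the chance of success is 99% at SD 15, 88% at SD 20, 61% at SD 25 and 31% at SD 30. For all six pairs at once, simulation gives about 97%, 61%, 18% and 2%.

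**The case against.** The aim is exploratory, carries no power claim and is framed as a comparison of yield. The Innovation section promises group-specific response rates, and logistic models may follow. Readers will therefore see the rates and can judge them. This stands: the aim is not unanswerable, and descriptive rates would be useful even without a formal test. It does not repair the p-values, or any intervals calculated as if messages were independent.

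Three stronger readings are tempting, and the documents do not support them.

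- **That the test is bound to reject for differences under one point.** That threshold applies to an observed gap between large groups compared in pairs, with about three seasons pooled. Over one season two communities need 1.45 points, and a 5% versus 95% split over three seasons needs 1.36. The plan relates response to community as a whole, which is a 3-df test. Treating messages as independent, that test detects a true 1-point range (equally spaced rates, three seasons) with only 53% power at 0.05 and 65% at 0.10.
- **That p<0.1 is the rule for accepting or rejecting similarity.** In the text it only decides whether multivariable models are built. No level is given for judging the hypothesis.
- **That similarity within 10 points could readily be shown.** The documents contain no such margin, and Step 5 shows that the rule often fails when households vary widely.

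The analyst might also intend to adjust for household in the logistic models. The text does not say so, and those models are reached only through the unadjusted screen.

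**Conclusion.** The concern holds as a minor point. The stated test cannot show the similarity that is hypothesised, and its error rates are wrong because messages are clustered in households. Clustering is the larger problem: false rejection of about 55% to 80% for two groups over three seasons, or 34% to 66% over one, at a nominal 5%.

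These figures rest on the assumed ICC of 0.05 to 0.30, on three seasons inferred from the timeline, and on equal message counts per household. Replacement of households (the plan expects 10-20% a year) would lower the count for some and move the result towards the one-season figures. The mismatch between hypothesis and test rests on no assumption.

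A reader might infer that the trial's main conclusions are at risk. They are not: the primary and secondary transmission analyses do not use this test.

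**What to change.** Replace the message-level chi-square, and any logistic model without a household term, with an analysis that respects the household. GEE, a mixed logistic model or a comparison of household-level response proportions would each do. Report the response rate in each group, and the differences between groups, with 95% confidence intervals.

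Then choose one of two courses before the data are examined:
- state and justify a margin, and conclude similarity only where the interval lies inside it; or
- reword the hypothesis as descriptive and let the estimates and intervals stand.

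The margin is for the sponsor to choose. The p<0.1 screen, if kept for model building, should use p-values from the clustered analysis.

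The cost is a change of SAP wording, with no new data. Intervals will be wider than the message-level analysis would give. With 100 households per community, a tight margin may leave some comparisons inconclusive, most likely if reporters vary widely in how often they reply.
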